The proposed work leverages the novel infrastructure of the Patient-Centered Outcomes Research Institute-funded PaTH Clinical Data Research Network (CDRN), a partnership of four Mid-Atlantic academic health systems (Penn State Hershey Medical Center, University of Pittsburgh Medical Center, Temple Health System, and Johns Hopkins Health System) that have established governance to operate as an integrated research network. In 2015, the University of Utah and Geisinger Health System also joined PaTH, creating an electronic health record (EHR)-based data infrastructure across three states (Maryland, Pennsylvania, and Utah).

[figure not shown]
We have additionally added a focus on rural/urban differences in provision of obesity screening and counseling and the resultant impact on weight loss and diabetes incidence. Rural populations have a 17% higher prevalence of diabetes when compared to their urban counterparts. As a result, diabetes is the second highest priority for Rural Healthy People 2020. Additionally, rural populations have lower rates of guideline-concordant diabetes services, although this has been inadequately investigated. Studies report adults with diabetes living in rural communities are less likely to receive adequate diabetes-related care than non-rural residents, but are limited in study design (i.e., reliant on patient self-report or medical expenditure data). We propose leveraging the novel infrastructure of the Patient-Centered Outcomes Research Institute-funded PaTH CDRN to understand the rural and urban effects on diabetes and its complications. The integration of six large health institutions spanning a diversity of rural and urban populations has the unique opportunity to overcome limitations of prior studies by using health record data. In this way, our proposed study will address important gaps in our understanding of rural/urban differences in diabetes outcomes and guide future approaches to address and eliminate disparities.

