Utilizing the PaTH CDRN offers an opportunity to study rural/urban effects, given that the 6 health institution network (University of Pittsburgh Medical Center, Penn State Hershey Medical Center, Temple Health System, Johns Hopkins Health System, University of Utah Health Care, and Geisinger Health System) covers significant populations in both rural and urban counties. For example, PaTH CDRN's service area includes more than 85% of the population of Pennsylvania, including coverage in nearly every one of Pennsylvania's 67 counties (48 rural and 19 urban, see map below). Further, 27% of Pennsylvania's residents live in rural counties, which is higher than the national average of 20%, offering opportunity to better understand diabetes care in this setting. The addition of the University of Utah also offers a different geographic location with similar opportunities to study rural/urban effects. This system provides care for Utahns and residents of five surrounding states in a referral area encompassing more than 10% of the continental US, the vast majority of which is rural. Johns Hopkins Health System, Temple Health System, and the University of Pittsburgh Medical Center offer three different urban populations for comparison.

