## 2.2 Previous Data

### *Preliminary Studies*

PaTH Clinical Data Research Network

**Overview.** The PaTH Clinical Data Research Network (CDRN) brings together four Mid-Atlantic academic health systems—the University of Pittsburgh/University of Pittsburgh Medical Center (UPMC), Penn State College of Medicine/Hershey Medical Center, Temple University School of Medicine/Temple Health, and the Johns Hopkins University/Johns Hopkins Health System/Johns Hopkins Health Care to function as an integrated research network and learning health system, providing an infrastructure for pragmatic clinical trials and observational studies that require populations beyond a single health system to answer important patient-centered clinical and health services questions ([www.pathnetwork.org](http://www.pathnetwork.org)). Funded by the Patient-Centered Outcomes Research Institute (PCORI) in March 2014, the PaTH CDRN is one of 11 CDRNs across the country. Along with 18 Patient-Powered Research Networks (PPRNs), these 11 CDRNs form PCORnet—the National Patient-Centered Clinical Research Network—a national network for conducting clinical outcomes research ([www.pcornet.org](http://www.pcornet.org)). The goal of PCORnet is to improve the nation’s capacity to conduct comparative effectiveness research by creating large, highly representative network from which to draw data, while protecting patient privacy and ensuring data security.

PaTH’s mission during its initial funding period is to create the technical, governance, and patient- and clinician-engagement infrastructure to conduct clinical and health services research across diverse health systems. For this proposal, we will include all four of the PaTH institutions (Pittsburgh, Penn State, Johns Hopkins, and Temple), thus representing patients from Pennsylvania and Maryland. The University of Utah will join the PaTH network in 2015, which is an exciting new partnership for our network (see Table 3). The addition of the University of Utah greatly strengthens the proposed project by adding a state that has not adopted Medicaid expansion.

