In the multi-level modeling, the first-level unit is the yearly measurement for the individual subject (pre- and post-policy), the second-level unit is the individual subject, the third-level unit is the health system or clinic within the health system (cluster), and the fourth-level unit is the state. We set year 2014 as time origin for Utah when considering the policy impact of the ACA. Let  $Y_{ijkt}$  denote the binary response of having controlled diabetes at year  $t$  since policy changes for the  $k^{\text{th}}$  subject within the  $j^{\text{th}}$  cluster of the  $i^{\text{th}}$  state,  $t = -5, -4, \dots, 0, 1, \dots, 5$ ,  $i = 1, 2, 3$ ;  $j = 1, 2, \dots, c_i$ , and  $k = 1, 2, \dots, n_{ij}$ , where  $c_i$  is the number of clusters within the  $i^{\text{th}}$  state and  $n_{ij}$  is the sample size within the  $j^{\text{th}}$  cluster of the  $i^{\text{th}}$  state. An individual subject may not be in the system for all 11 timepoints of measurement, so  $t$  will have a smaller range of values for that individual subject. Also due to the different timeline of policy changes, the number of years before and after policy changes may vary. The probability of having controlled diabetes,  $\mu_{ijkt} = E(Y_{ijkt}) = \Pr[Y_{ijkt} = 1]$ , can be described by the following segmented logistic regression model

$$\begin{aligned} \text{logit } \mu_{ijkt} &= \log \{\Pr[Y_{ijkt} = 1] / \Pr[Y_{ijkt} = 0]\} \\ &= \beta_{0ijk} + (t + 5) \beta_{1ijk} && \text{if } -5 \leq t \leq 0, \text{ pre-period before policy changes} \\ &= \beta_{0ijk} + 5 \beta_{1ijk} + t \beta_{2ijk} && \text{if } 0 \leq t \leq 5, \text{ post-period after policy changes} \end{aligned}$$

where  $\beta_{mijk}$  ( $m = 0, 1, 2$ ) are subject-specific regression parameters, with  $\beta_{0ijk}$  being the log odds of having controlled diabetes at  $t = -5$ , and  $\beta_{1ijk}$  and  $\beta_{2ijk}$  being the slopes (annual change in log odds) for the pre- and post-periods, respectively. In the framework of a mixed-effects model, each  $\beta_{mijk}$  is modeled by

$$\beta_{mijk} = \mathbf{x}_{mijk}^T \boldsymbol{\beta}_m + \mathbf{z}_{ij}^T \boldsymbol{\gamma}_{1ij} + \boldsymbol{\gamma}_{2mijk}$$

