where  $\mathbf{x}_{mijk}$  is the vector of regressors for the fixed effects,  $\boldsymbol{\beta}_m$  is the corresponding vector of fixed-effects parameter coefficients,  $\mathbf{z}_{ij}$  is a vector of cluster-level regressors for the random effects for the  $j^{\text{th}}$  cluster of the  $i^{\text{th}}$  state,  $\boldsymbol{\gamma}_{1ij}$  is the cluster-level random-effect coefficients and is common to all  $m$ , and  $\boldsymbol{\gamma}_{2mijk}$  is the subject-level random-effect coefficients associated with the parameter  $\beta_m$  for the  $k^{\text{th}}$  subject within the  $j^{\text{th}}$  cluster. The random effects are assumed to follow a multivariate normal distribution with mean zero. Because the vector  $\mathbf{x}_{mijk}$  may include subject-level, cluster-level and state-level exposure variables, the fixed effects parameter vectors  $\boldsymbol{\beta}_1$  and  $\boldsymbol{\beta}_2$  represent the effects of different exposure variables on the annual changes in the pre- and post-periods. Thus, we may perform statistical tests to examine whether there are differences in trends between the pre- and post-periods overall and for each state, and whether the patterns of changes differ between the states.

Similarly for a count outcome  $Y_{ijkt}$  (e.g., number of clinical visits), we define the expected value  $\mu_{ijkt} = E(Y_{ijkt})$  and apply a Poisson regression model based on the natural log link function. The log expected number of clinical visits,  $\log(\mu_{ijkt})$ , can be modeled with the aforementioned segmented mixed-effects model. The use of an offset term in the models yields the estimates of the rate of clinical visits rather than the mean number of visits. The fixed-effect parameters,  $\beta_1$  and  $\beta_2$ , represent the effects of exposure variables on the annual changes in log of incidence rates for the pre- and post-periods, respectively. For a continuous outcome  $Y_{ijkt}$ , we will model the mean,  $\mu_{ijkt} = E(Y_{ijkt})$ , with the mixed-effects model and the parameters  $\beta_1$  and  $\beta_2$  indicate the effects of exposure variables on the annual changes in the outcomes for the pre- and post-periods, respectively. All final statistical models will be assessed with respect to the goodness-of-fit and the appropriateness of model assumptions. Statistical software SAS 9.4 and R environment will be used to implement the proposed analyses.

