*Statistical Power.* Given the very large sample sizes that are anticipated for the research studies (more than 320,000 patients with diabetes and 2,000,000 patients at-risk for diabetes), there is tremendous statistical power to detect very small effect sizes for individual-level exposure variables. Therefore, the clinical investigators on this project will need to

examine each statistically significant result and determine whether it is clinically significant. Furthermore, such large sample sizes ensure the robust estimation results from the proposed multi-level statistical modeling which involves large number of regression coefficient and covariance parameters. The major benefit of the large sample size for each research study is that it provides sufficient statistical power for investigating effects of interest within subgroups that might be constructed according to age, race-ethnicity, cohort decompositions, etc.

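### Utah, and apparently Maryland, is represented by a single health system, so the optional tests of state differences in trend cannot separate state from system, and patient numbers do not make system-level estimates robust

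*Combined protocol and SAP*

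**What the plan says.** Section 8.0 sets out a four-level model. Yearly measurements lie within patients, and above the patient "the third-level unit is the health system or clinic within the health system (cluster), and the fourth-level unit is the state". After giving the equations, it says the team may test for differences between pre- and post-period trends, overall and by state, and "whether the patterns of changes differ between the states".

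The Statistical Power paragraph at the end of section 8.0 confines its power claim to exposures measured on individuals. It then adds, without that limit, that "such large sample sizes ensure the robust estimation results from the proposed multi-level statistical modeling", and refers to the model's many regression and covariance parameters.

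On the sites, section 2.1 describes a "data infrastructure across three states (Maryland, Pennsylvania, and Utah"). Section 2.2 (Preliminary Studies) lists the original four systems as ("Pittsburgh, Penn State, Johns Hopkins, and Temple), thus representing patients from Pennsylvania and Maryland". Section 2.1 adds: "In 2015, the University of Utah and Geisinger Health System also joined PaTH". Section 2.2 values Utah for "adding a state that has not adopted Medicaid expansion", and section 8.0 sets 2014 as the time origin for Utah when the impact of the ACA is considered.

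**The concern.** A state comparison needs more than one independent unit per state. If a state has only one health system, anything that changed over time in that system and not elsewhere looks the same as an effect of the state. Examples are a new counseling program, a change in recording, or a change in the population served.

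The protocol presents Utah as a contrast on Medicaid expansion. A Utah difference in slope change could therefore be reported as a state policy effect when it belongs to one institution. Utah patients are not a clean sample of Utah policy either: section 2.1 says "This system provides care for Utahns and residents of five surrounding states".

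The robustness sentence adds to the risk because it suggests that patient numbers settle precision at every level. No part of the document gives the number of systems per state as a limitation.

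**Working it through.** **The plan's own figure.** The only quantitative basis for power and robustness is the number of patients. The site columns in section 7.2 reproduce it:

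- Diabetes: 25,219 + 150,589 + 60,324 + 40,536 + 51,787 = 328,455.
- At risk: 167,799 + 950,020 + 471,860 + 212,314 + 260,506 = 2,062,499.

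No significance level, effect size, intraclass correlation or number of clusters is given.

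**Systems per state (inferred from sections 2.1 and 2.2; no table lists it).**

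| State | Systems | Diabetes cohort, tabulated |
|---|---|---|
| Pennsylvania | Pittsburgh, Penn State, Temple, Geisinger (not tabulated) | 216,344 |
| Maryland | Johns Hopkins | 60,324 |
| Utah | University of Utah | 51,787 |

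The 216,344 is 25,219 + 150,589 + 40,536. Geisinger's state is not given. If Geisinger were in Maryland, the total degrees of freedom below would be the same but one would come from Maryland. Utah would still have one system.

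**If the third level is the system.** Error degrees of freedom for a state comparison = systems − states. Write τ for the between-system SD of the slope change, and assume it is the same in every state.

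- Six systems: 6 − 3 = 3. By state this is (4 − 1) + (1 − 1) + (1 − 1), so all three come from Pennsylvania. t(0.975, 3) = 3.18.
- Five tabulated systems: 5 − 3 = 2. t(0.975, 2) = 4.30.
- 95% limits for τ as multiples of its estimate, √(df/χ²(0.975)) and √(df/χ²(0.025)): 0.57 and 3.7 with 3 df; 0.52 and 6.3 with 2 df.

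With unlimited patients, the standard error of a contrast does not fall below τ√(1/k₁ + 1/k₂), where k₁ and k₂ are the numbers of systems in the two states. The true difference needed for 80% power (two-sided 5%, noncentral t) is:

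| Contrast | SE, six systems | Needed, six systems | SE, five systems | Needed, five systems |
|---|---|---|---|---|
| Pennsylvania vs one single-system state | 1.12τ | 4.8τ | 1.15τ | 6.5τ |
| Maryland vs Utah | 1.41τ | 6.0τ | 1.41τ | 8.0τ |

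**If the third level is the clinic.** Let each of two single-system states have C clinics with clinic-level SD ω. The variance of their contrast is 2τ² + 2ω²/C + a patient term. More clinics and patients shrink the last two parts but not 2τ². A model with clinics and no system term leaves 2τ² out, so the aliasing remains.

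**Do systems within one state differ?** In the section 7.2 table, the Medicaid share of the diabetes cohort is 8%, 7% and 54% at Penn State, Pittsburgh and Temple, against 1% at Johns Hopkins and 8% at Utah. The spread within Pennsylvania exceeds the Maryland–Utah gap. Covariates can adjust for measured mix of this kind, but not for unmeasured system-specific changes over time.

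**A related inconsistency.** The at-risk cohort definition in section 7.2 speaks of four institutions, while the table there has five, including Utah. These need reconciling, since on the first reading Utah might not be represented in that cohort.

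**The case against.** The strongest reply is that the test is optional and peripheral. Section 8.0 says only that such tests may be done, and neither aim contains a between-state hypothesis. Section 2.1 describes the counseling benefit as CMS coverage followed by universal insurer coverage, not as a state measure. All of this stands and lowers the weight of the point. It does not make the test interpretable if it is run.

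Stable differences in level between systems also largely drop out of a comparison of slope changes. This stands too: only system-specific changes over time confound.

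A reader might infer that the state test will give a tiny p-value because it rests on patients. The documents do not support that as a flat statement. The written model has a cluster effect that enters both slopes as well as the intercept, so a system-level version is not purely patient-based. The effect is constrained to be the same for all three coefficients; read literally, it cancels from the post-minus-pre slope. That supports giving the slopes variance terms of their own, but without an intraclass correlation or a degrees-of-freedom method no p-value can be predicted.

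Two other tempting supports fail. The documents do not say that a system's clinics share coding practice or management; they describe diverse affiliated practices. Nor does EHR platform separate Maryland from Utah, since Table 3 lists Epic for both.

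Finally, the power claim itself is properly limited to individual-level exposures. Only the robustness sentence overreaches. It does so at system level: the written equation has no state random effect, so no state variance is there to be badly estimated.

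**Conclusion.** The point holds in a limited form. Utah, and on the inferred mapping Maryland, cannot be distinguished from one health system in any test of state differences in trend, whichever unit is the third level. With systems as units there are about 3 error degrees of freedom (2 for the tabulated systems), all from Pennsylvania, and the between-system SD is known only to within about 0.57 to 3.7 times its estimate. These figures assume the system reading, six systems with Geisinger in Pennsylvania, and a common between-system SD. If clinics are the clusters and are numerous, clinic-level variances may be well estimated, but the aliasing stays.

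A reader might infer that the main pre/post results are also undermined. They are not on this ground: within-system slope changes and patient-level effects do not depend on separating state from system.

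**What to change.** In the model description in section 8.0:

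- Fit health system as a fixed factor with its own pre- and post-slopes. Use clinic as the random cluster, with a clinic-level slope variance of its own.
- Report slope changes by system, with the Pennsylvania systems also averaged.
- Present any between-state contrast as a descriptive between-system contrast, and do not attribute it to state policy. If p-values are shown for system differences, say that they concern these particular systems.

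In the Statistical Power paragraph, limit the robustness sentence to patient-level effects, and to clinic-level variances if there are many clinics. State that precision at system and state level depends on the number of systems, not patients.

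Also state which system belongs to which state, and reconcile the number of institutions across sections.

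The cost is a wording change and a modest change to the model. The team gives up the optional formal state test and the separate estimation of state-level exposures that do not vary over time. The design can support neither.

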***At-risk Cohort Definition.*** The cohort of patients under study will be defined as patients age 18 and older who are at risk for the development of diabetes, based on being overweight. Patients seen at one of the four PaTH institutions will be included in the at-risk cohort if they have a  $BMI \geq 25 \text{ kg/m}^2$ , based on most recent recorded weight and at least one recorded height. The at-risk cohort will be further limited to patients who will likely to be captured in the PaTH EHR records or claims data so that outcome assessments can occur. Thus, we will further limit the at-risk cohort to patients who have either: (1) had at least 2 outpatient primary care visits in one of the PaTH health systems in the past 3 years (since January 1, 2012), or (2) for whom claims data is available. The cohort will be dynamic, with new patients added into the cohort after 2015 as they meet the at-risk cohort definition prospectively. Patients will not be removed from the cohort, even if they are no longer overweight. The observational period for the outcome variables will be for the 10-year period from 2009-2019, thus including 3 years of data prior to the first policy change (CMS instituting coverage for intensive behavioral therapy for obesity) and 3 years after the last policy change (Pennsylvania Medicaid expansion) under study.

[figure not shown]
intensive behavioral therapy for obesity) and 3 years after the last policy change (Pennsylvania Medicaid expansion) under study.

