**Table 1. Proposed Outcomes for the Pre-diabetes and Diabetes Cohorts**

Outcomes	Definition	Notes
Pre-diabetes cohort		
Weight loss during counseling	Weight lost from first IBT visit to final IBT visit	Available at all PaTH sites
Weight loss maintenance	% of weight lost during program and maintained over remaining time period, reported by year	Available at all PaTH sites
Diabetes incidence	% of patients who develop diabetes per year following weight counseling	Available at all PaTH sites
Patient-reported outcomes	-SF-12 -PHQ-2, PHQ-8, PHQ-9 -Physical function -sleep -fruit and vegetable consumption -social support -physical activity -PROMIS (PROMIS 29, physical function, depression) -healthy lifestyles -patient reported medication reconciliation	Available at some sites – Formal inventory of PROs will be collected at each institution at the beginning of the project, to be included as secondary outcomes
Diabetes cohort		
Weight loss during counseling	Weight lost from first IBT visit to final IBT visit	Available at all PaTH sites
Weight loss maintenance	% of weight lost during program and maintained over remaining time period, reported by year	Available at all PaTH sites
Patient reported outcomes	-SF-12 -PHQ-2, PHQ-8, PHQ-9 -Physical function -sleep -fruit and vegetable consumption -social support -physical activity -PROMIS (PROMIS 29, physical function, depression) -healthy lifestyles -patient reported medication reconciliation	Available at some sites – Formal inventory of PROs will be collected at each institution at the beginning of the project, to be included as secondary outcomes
Uncontrolled diabetes	Average A1c > 9 or no A1c	Available at all PaTH sites
Controlled blood pressure	SBP < 140, DBP < 90, averaged across values over year	Available at all PaTH sites
On a statin medication	Evidence of a statin medication on current EHR medication list	Available at all PaTH sites
Receiving annual eye exam	Documentation of eye exam once in past year	Available at all PaTH sites
Receiving annual urinary microalbumin test	Documentation of lab testing for urinary microalbumin at least once in past year	Available at all PaTH sites
Lower extremity amputations	Documentation of procedure for lower extremity amputation or billing code through health plans in past year	Available at all PaTH sites

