Furthermore, we will use the similar models as described above to evaluate post-policy impact of obesity screening and counseling (number of visits) on the outcomes such as weight loss, diabetes incidence, and diabetes outcomes (including hemoglobin A1c, controlled blood pressure, use of a statin medication). The outcome data collected after the universal coverage change (i.e.,  $t = 0, 1, \dots, 6$ ) will be used to estimate the trend of change. The number of screening and counseling will be used as a predictor in the mixed effects models. The effects of patient and practice characteristics will also be examined in the models. Statistical software SAS 9.4 and R environment will be used to implement the proposed analyses.

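### Diabetes incidence is assigned to a yearly mixed-effects model built for a repeatable state, with no diabetes-free risk set, so its trend can be distorted

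*Combined protocol and SAP*

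**What the plan says.** Diabetes incidence is named in both Aim 1 and Aim 2 (section 1.0). Table 1 in section 7.2 defines it for the pre-diabetes cohort as the percentage "of patients who develop diabetes per year following weight counseling". The denominator is patients; the table does not say that they must still be free of diabetes.

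Section 8.0 assigns the method: "we will use the similar models as described above to evaluate post-policy impact of obesity screening and counseling", measured by number of visits, "on the outcomes such as weight loss, diabetes incidence, and diabetes outcomes", with incidence listed beside weight loss, A1c, blood pressure and statin use. "The outcome data collected after the universal coverage change", at t = 0 to 6, serves to estimate a trend, and the number of counselling contacts enters as a predictor.

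The model referred to is set out earlier in section 8.0 for controlled diabetes. There "the first-level unit is the yearly measurement for the individual subject", and the intercept and both slopes are "subject-specific regression parameters", each with its own subject-level random effect. An offset is described only for counts such as visits.

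The documents do not end a patient's incidence records at first diagnosis, restrict the analysis to diabetes-free years, or name a hazard or time-to-event model. The only exclusion criterion (section 3.2) is age under 18.

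**The concern.** Controlled diabetes can be present one year, absent the next and present again, so a yearly record per patient with a patient-specific trajectory makes sense. Onset of diabetes happens once. After it, the patient is no longer at risk and has nothing further to contribute to an incidence rate. A plan that does not say what happens to later records leaves the estimand open.

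Two consequences follow. If patients who have converted stay in the denominator, the yearly proportion falls as they accumulate, even when the hazard among those still at risk is constant. If records do stop at onset, no patient has more than one event. There is then no within-patient repetition from which to learn a subject-level variance, and the fitted trend depends on what that variance is taken to be.

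The trend is one of the quantities section 8.0 says it will estimate. Its Statistical Power paragraph expects very small effects to be detectable, so a small artefact could be reported as significant.

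**Working it through.** The plan states no incidence rate, effect size, alpha or power for this outcome, so there is no figure to reproduce.

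**Inputs.** Years t = 0 to 6 (section 8.0). At-risk cohort 2,062,499 (section 7.2). The annual hazard h is not in the documents and is assumed constant, from 0.5% to 10%. I also assume a closed cohort, diabetes-free at t = 0, with no deaths. The true trend is therefore zero.

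**Step 1: trend under the codings left open.** I fitted logit = a + b·t to expected counts, without random effects.

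- Records stopped at onset: proportion h every year, so b = 0.
- Onset year coded 1, later years 0: proportion h(1 - h)^t.
- Status carried forward: proportion 1 - (1 - h)^(t+1).

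| h | Onset-year proportion, t = 0 to t = 6 | Slope, onset-year coding | OR per year | Slope, carried forward |
|---|---|---|---|---|
| 0.5% | 0.500% to 0.485% | -0.005 | 0.995 | +0.268 |
| 1% | 1.00% to 0.94% | -0.010 | 0.990 | +0.271 |
| 2% | 2.00% to 1.77% | -0.021 | 0.980 | +0.278 |
| 4% | 4.00% to 3.13% | -0.042 | 0.959 | +0.292 |
| 5% | 5.00% to 3.68% | -0.054 | 0.948 | +0.299 |
| 10% | 10.0% to 5.3% | -0.114 | 0.892 | +0.339 |

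Hand check at 4%: logit(0.0400) = -3.178 and logit(0.0313) = -3.432; the difference, -0.254, divided by 6 is -0.042. Over six years the false odds ratio is exp(6 × -0.0206) = 0.88 at 2% and exp(6 × -0.0423) = 0.78 at 4%. Adding a random intercept to onset-year coding does not help: at 2% and 5% its SD is estimated as 0 and the slopes stay at -0.021 and -0.054.

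**Step 2: the counselling contrast.** Suppose counselling multiplies the annual risk by 0.80 (assumed). The odds ratio with a risk set, then under onset-year coding, is:

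- h = 2%: 0.797, then 0.807; ln 0.807 / ln 0.797 = 0.945, so about 6% attenuation on the log scale.
- h = 5%: 0.792, then 0.817; ratio 0.867, about 13%.
- h = 10%: 0.783, then 0.837; ratio 0.727, about 27%.

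**Step 3: records stopped at onset, subject-level intercept kept.** The data have no true heterogeneity and a true slope of -0.10. I fixed the subject SD and refitted, using expected counts and 60-point quadrature. Scaling from 100,000 patients to the full cohort multiplies the deviance cost by 2,062,499 / 100,000 = 20.62.

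| Starting hazard | Subject SD | Fitted slope | Deviance cost per 100,000 | Cost at 2.06 million |
|---|---|---|---|---|
| 4% | 0 | -0.100 | 0 | 0 |
| 4% | 0.5 | -0.092 | 0.04 | about 0.8 |
| 4% | 1.0 | -0.064 | 1.37 | about 28 |
| 2% | 1.0 | -0.080 | 0.19 | about 4 |

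With a constant 2% hazard, SD = 1 moves the slope from 0 to +0.027 at a cost of about 0.0004 per 1,000 patients. At full size that is about 0.0004 × 2,062 = 0.8, too little to tell the two fits apart.

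**The case against.** The strongest reply is that section 8.0 promises similar models, not identical ones. It lets a patient contribute fewer years than the full range and requires model assumptions to be assessed, and section 7.2 foresees settling the analysis models after an early extraction. A yearly logistic regression whose records end at onset already is a discrete-time hazard model. This much stands: the logistic form is not the fault, and a team that restricted to diabetes-free years would recover the right trend once the subject-level effects were dealt with. But the text does not state that restriction. The allowance for fewer years concerns patients who are not in the system, not patients who have had the event.

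A reader might infer more than the documents support:

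- **That the model would show incidence rising steeply.** The slopes of +0.27 to +0.34 require diabetes status to be carried forward, which is prevalence. Table 1 counts patients who develop diabetes in a year, so this coding conflicts with it.
- **That the plan orders converted patients to be kept.** Section 7.2 says "Patients will not be removed from the cohort, even if they are no longer overweight". That rule is about weight and does not address onset.
- **That the subject variance cannot be determined at the planned size.** At a 4% hazard, SD = 1 would cost about 28 deviance units in 2.06 million patients and be rejected. At 2% the cost is about 4, which is borderline, and the analysed cohort may be smaller. The difficulty is weaker at scale but not removed.
- **That incidence is the principal outcome.** No primary outcome is named, and the hypotheses stated under Aim 1 concern receipt of counselling and weight loss.

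**Conclusion.** The concern holds as a should-fix. As written, the plan does not determine what is estimated for an outcome named in both aims. The literal route, with onset-year coding and all patients kept, produces a false decline of about -0.005 to -0.042 log-odds per year at hazards of 0.5% to 4%, and -0.11 at 10%. The artefact is small at the low end. The counselling contrast suffers much less, with about 6% attenuation on the log scale at 2% and more at higher hazards.

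Ending records at diagnosis removes this artefact but not the dependence of the slope on subject-level random effects. With one event at most per patient, their variance is identified only through the assumed shape of the trend and the assumed random-effect distribution.

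These sizes rest on an assumed constant hazard and a closed cohort. The study's cohort is dynamic, and new diabetes-free entrants would dilute the false decline. Step 3 examined a random intercept only; the random slopes in the plan were not checked.

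**What to change.** In section 8.0, give diabetes incidence its own model:

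- A discrete-time hazard model, pooled logistic or complementary log-log.
- One record per diabetes-free year, ending at first diagnosis, death or last contact.
- Number of counselling visits as a time-varying predictor.
- No subject-level random intercept or slopes.
- Clinic-level clustering retained, by a random effect or clustered standard errors.

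In Table 1, define the outcome per diabetes-free person-year.

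The cost is a change of wording: no additional outcome is needed, and the model is simpler and faster to fit than the stated one. The downsides are that one outcome takes a different model form from the rest, and that its estimates are population-average at the patient level. Dropping the subject effects does not separate depletion of high-risk patients from a true fall in individual risk; it makes the population-level hazard the stated target, and the report should say so.
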